#### 6.4.1.2 *AE Overview*

An AE overview without SOC and PT presents the number and percentage of subjects with any the following AEs: any AE; mild AE; moderate AE; severe AE; moderate or severe AE; AE related to study drug; AE leading to study drug discontinuation; SAE; SAE related to study drug; SAE leading to study drug discontinuation; potential drug abuse AE; medication-overuse headache AE; hepatic-related AE; local irritation AE; cardiovascular AE; and suicidality AE.

An AE overview is produced for each the following analysis periods and analysis sets:

- Pre-treatment AEs for the enrolled analysis set
- Pre-treatment AEs for the safety analysis set
- On-treatment AEs for the safety analysis set
- On-treatment AEs for the safety analysis set by subgroup level and overall for all subgroups of interest specified in Section 4.3
- TEAEs for the safety analysis set
- Follow-up AEs for the follow-up analysis set.

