### 4.3 Subgroups

The following safety subgroups are of interest for the safety analysis set:

- Intrinsic factors
  - Age at informed consent (years):  $< 40$ ,  $\geq 40$ ,  $< 65$ ,  $\geq 65$
  - Sex: female, male
  - Race: White, Black or African American, other including Asian, Asian
  - Ethnicity: Hispanic or Latino, not Hispanic or Latino
  - Cardiovascular risk factors contraindicating triptans: yes, no (refer to the Zavegeptan Core SAP)
  - Baseline body mass index (BMI;  $\text{kg}/\text{m}^2$ ):  $< 25$ ,  $\geq 25$  to  $< 30$ ,  $\geq 30$

- Extrinsic factors
  - Average zavegepant exposure (sprays per month): < 6,  $\geq$  6 (see Section 6.2.5.1).
  - Cumulative zavegepant exposure (sprays): < 20,  $\geq$  20 to < 40,  $\geq$  40 to < 60,  $\geq$  60 to < 80,  $\geq$  80 (see Section 6.2.5.1)
  - Time on zavegepant (weeks): < 12,  $\geq$  12 to < 24,  $\geq$  24 to < 36,  $\geq$  36 to 48,  $\geq$  48 (see Section 6.2.5.1)
  - Concomitant prophylactic migraine medication use: yes, no (see Section 6.2.5.4)
  - Current or concomitant approved biologics use (yes, no; see Section 6.2.5.4)
  - Total treated migraine days per month in the overall LTT (< 2,  $\geq$  2; see Section 6.4.6.2).

Subgroup tables present results by subgroup level and overall for subjects with non-missing subgroup level data. Subgroup levels may be redefined or combined based on the availability of data.

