### **eDiary Zavegepant and LTT Exposure**

eDiary zavegepant and LTT exposure is tabulated as continuous or categorical variables for the safety analysis set, and includes the following parameters:

- Time in the OP (weeks), derived as  $(OP\ end\ date - OP\ start\ date + 1)/7$
- Time from LTT start to last contact (weeks), derived as  $(last\ contact\ date - LTT\ start\ date + 1)/7$
- Time in the LTT period (weeks), derived as  $(LT\ end\ date - LT\ start\ date + 1)/7$
- Time in the LTT period (weeks) categories:  $\geq 11$ ,  $\geq 23$ ,  $\geq 51$ . These correspond to using a 1-week lower bound on 3, 6, and 12 months, respectively.
- Time on zavegepant (weeks), derived as  $(study\ drug\ end\ date - study\ drug\ start\ date + 1)/7$
- Time on zavegepant (weeks) categories:  $<12$ ,  $\geq 12$  to  $< 24$ ,  $\geq 24$  to  $< 36$ ,  $\geq 36$  to  $< 48$ ,  $\geq 48$ . These align with subgroups specified in Section 4.3.
- Cumulative zavegepant exposure (sprays), derived by summing number of sprays across records with complete study drug dates
- Cumulative zavegepant exposure (sprays) categories:  $< 20$ ,  $\geq 20$  to  $< 40$ ,  $\geq 40$  to  $< 60$ ,  $\geq 60$  to  $< 80$ ,  $\geq 80$ . These align with subgroups specified in Section 4.3.
- Average zavegepant exposure (sprays per month), derived as (1) cumulative zavegepant exposure (sprays) if time in the LTT period  $< 2$  weeks, or (2)  $4 \times$  cumulative zavegepant exposure/time in the LTT period if time in the LTT period  $\geq 2$  weeks.
- Average zavegepant exposure (sprays per month) categories:  $< 6$ ,  $\geq 6$ . These align with subgroups specified in Section 4.3.
- Number and percentage of subjects who administered  $> 1$  spray on any 1 day
- Number and percentage of subjects who administered  $> 8$  sprays per month in any month
- Exposure categories, defined as the number and percentage of subjects who administered
  - $\geq 1$  spray per month for 1, 2, 3, 4, 5,  $\geq 12$ ,  $\geq 6$ ,  $\geq 3$  and  $\geq 1$  months
  - $\geq 2$  sprays per month for 1, 2, 3, 4, 5,  $\geq 12$ ,  $\geq 6$ ,  $\geq 3$  and  $\geq 1$  months
  - $\geq 3$  sprays per month for 1, 2, 3, 4, 5,  $\geq 12$ ,  $\geq 6$ ,  $\geq 3$  and  $\geq 1$  months

- $\geq 4$  sprays per month for 1, 2, 3, 4, 5,  $\geq 12$ ,  $\geq 6$ ,  $\geq 3$  and  $\geq 1$  months
- $\geq 5$  sprays per month for 1, 2, 3, 4, 5,  $\geq 12$ ,  $\geq 6$ ,  $\geq 3$  and  $\geq 1$  months

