- $\geq 6$  sprays per month for 1, 2, 3, 4, 5,  $\geq 12$ ,  $\geq 6$ ,  $\geq 3$  and  $\geq 1$  months
- $\geq 7$  sprays per month for 1, 2, 3, 4, 5,  $\geq 12$ ,  $\geq 6$ ,  $\geq 3$  and  $\geq 1$  months
- $\geq 8$  sprays per month for 1, 2, 3, 4, 5,  $\geq 12$ ,  $\geq 6$ ,  $\geq 3$  and  $\geq 1$  months.
- Total zavegepant exposure (sprays) summed across all subjects, derived by summing cumulative exposure across all subjects
- Total zavegepant exposure (patient-years), derived by summing (study drug end date – study drug start date + 1)/365.25 across all subjects.

See Section 7.1 for derived dates.

eDiary zavegepant and LTT exposure is also tabulated by subgroup level and overall for the safety analysis set for all subgroups of interest described in Section 4.3.

Months are 4-week (28-day) intervals in the LTT analysis period defined as follows:

- Month 1 ( $\leq 4$  weeks; study days 1 to 28)
- Month 2 ( $> 4$  to  $\leq 8$  weeks; study days 29 to 56)
- Month 3 ( $> 8$  to  $\leq 12$  weeks; study days 57 to 85)
- Month 4 ( $> 12$  to  $\leq 16$  weeks; study days 85 to 112)
- Month 5 ( $> 16$  to  $\leq 20$  weeks; study days 113 to 140)
- Month 6 ( $> 20$  to  $\leq 24$  weeks; study days 141 to 168)
- Month 7 ( $> 24$  to  $\leq 28$  weeks; study days 169 to 196)
- Month 8 ( $> 28$  to  $\leq 32$  weeks; study days 197 to 224)
- Month 9 ( $> 32$  to  $\leq 36$  weeks; study days 225 to 252)
- Month 10 ( $> 36$  to  $\leq 40$  weeks; study days 253 to 280)
- Month 11 ( $> 40$  to  $\leq 44$  weeks; study days 281 to 308)
- Month 12 ( $> 44$  to  $\leq 48$  weeks; study days 309 to 336)
- Month 13 ( $> 48$  to  $\leq 52$  weeks; study days 337 to 364)
- Month 14 ( $> 52$  to  $\leq 56$  weeks; study days 365 to 392).

See Section 7.3 for the definition of study days.

Exposure categories assess the number of months in which a subject exceeded select spray counts in the LTT analysis period (see Section 7.2), where the number of months are not necessarily consecutive. For example, suppose a subject administers 4 sprays in Month 1, 3 sprays in Month 2, 5 sprays in Month 3, 6 sprays in Month 4, and 0 sprays in Month 5. Thus, this

subject is considered to have administered  $\geq 2$  sprays per month for 4 months (i.e., Months 1 through 4),  $\geq 4$  sprays per month for 3 months (i.e., Months 1, 3 and 4), and  $\geq 6$  sprays per month for 1 month (i.e., Month 4).

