#### 6.4.1.4 *On-treatment AEs*

On-treatment AEs are tabulated for the safety analysis set by SOC and PT for the following endpoints:

- AEs by intensity \*
- AEs occurring with  $\geq 5\%$  frequency by intensity (primary safety endpoint). The 5% cut applies only to total intensity.
- AEs occurring with  $\geq 10\%$  frequency
- TEAEs by intensity

- TEAEs occurring with  $\geq 2\%$  frequency after rounding. Percentages are displayed rounded to integers, and AEs are displayed in alphabetical order by SOC and PT.
- AEs related to study drug by intensity \*
- AEs by relationship to study drug (related, possibly related, unlikely related, not related, not reported)
- SAEs (primary safety endpoint)
- AEs leading to study drug discontinuation (primary safety endpoint)
- AEs of special interest
  - Potential drug abuse AEs, displayed in alphabetical order by intensity and PT without SOC (exploratory safety endpoint)
  - Medication-overuse headache AEs (exploratory safety endpoint)
  - Hepatic-related AEs by intensity (exploratory safety endpoint)
  - Local irritation AEs by intensity (exploratory safety endpoint)
  - Cardiovascular AEs
  - Suicidality AEs
- Exposure-adjusted multiple occurrences of unique AEs
- Exposure-adjusted multiple occurrences of unique SAEs
- Exposure-adjusted multiple occurrences of unique SAEs related to study drug
- Exposure-adjusted multiple occurrences of unique non-SAEs occurring with  $\geq 5\%$  frequency.

Endpoints marked with “\*” are also tabulated by subgroup level and overall for all subgroups of interest specified in Section 4.3.

Calculations for on-treatment exposure-adjusted multiple occurrences of unique AEs set the reference start date to the study drug start date, reference end date to the study drug end date, and reference last date to the study drug last date + 7 days.

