#### 6.4.2 Laboratory Tests

Laboratory tests are analyzed using results from the external central laboratory **CCI** [REDACTED] which identifies expired kits, and from local laboratory tests reported on CRFs. The central laboratory reports both laboratory collection date and time, whereas CRFs capture only laboratory collection date.

Laboratory tests of clinical interest are collected at the following visits:

- Hematology: Screening; Pre-Baseline; Weeks 4, 24, and 52; and early termination.
- Serum chemistry (including LFTs and lipids): Screening; Pre-Baseline; Weeks 4, 24, and 52; and early termination. Exceptions are for the following:
  - LFTs (ALT, AST, ALP, TBL, direct bilirubin, indirect bilirubin): Screening; Pre-Baseline; all visits during the treatment period; early termination; and Follow-up Week 2.
  - Lipids (total cholesterol, high-density lipoprotein [HDL] cholesterol, low-density lipoprotein [LDL] cholesterol, triglycerides): Pre-Baseline; Weeks 24 and 52; and early termination.
- Urinalysis: Pre-Baseline; Week 52; and early termination.

Clinically significant laboratory abnormalities are identified as grade 3 to 4 laboratory test results. Refer to the Zavegeptan Core SAP for laboratory tests of clinical interest for analyses, including identification of those with toxicity grades.

The following by-subject laboratory test listings are provided for the enrolled analysis set:

- Select laboratory test groups: hematology (both SI and US units)\*; serum chemistry, including LFTs (both SI and US units)\*; urinalysis (US units only)\*; pregnancy (US units only)\*; endocrinology, serology, drug screen, and miscellaneous laboratory tests (US units only). The pregnancy listing identifies positive pregnancy tests, which are defined as serum or urine pregnancy tests with either (a) “positive” character value, or (b) numeric value  $\geq 25$  U/L.
- LFT values and ratios to ULN (i.e., ALT, AST, TBL and ALP) for both US and SI units\*. The listing displays all LFT results over time for subjects with select LFT elevations (ALT or AST  $> 3$  x ULN; ALP or TBL  $> 2$  x ULN) at any time point.

- Creatine kinase (CK) elevation questionnaire.

Listings display toxicity grades and identify expired kits from the central laboratory, if applicable, and those marked with “\*” display COVID-19 visit impact code for visits impacted by COVID-19 (see Section 9.1.5.2). Refer to the Zavegeptan Core SAP for listing contents.

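### Crude AE percentages by final time on zavegepant and final cumulative sprays partly measure length of observation and AE-driven stopping, so they cannot be read as an effect of exposure

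*SAP*

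**What the plan says.** SAP 4.3 lists among its extrinsic safety subgroups "Time on zavegepant (weeks): < 12" weeks and upward, "Cumulative zavegepant exposure (sprays): < 20" and upward, average sprays per month, and "Total treated migraine days per month in the overall LTT". All are known only after treatment has run its course.

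Three sets of tables give numbers and percentages of subjects by every SAP 4.3 subgroup:
- the AE overview (6.4.1.2), specified as "On-treatment AEs for the safety analysis set by subgroup level and overall for all subgroups of interest specified in Section 4.3", which includes a row for AEs leading to study drug discontinuation;
- two starred rows of 6.4.1.4, AEs by intensity and related AEs by intensity, which "are also tabulated by subgroup level and overall for all subgroups of interest specified in Section 4.3";
- the starred table of worst on-treatment grade for each graded laboratory test (6.4.2.1).

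In SAP 6.2.6.1, "Time on zavegepant (weeks), derived as" last dose date minus first dose date plus 1, divided by 7. SAP 7.2 runs the on-treatment safety period from the first dose to the study drug last date plus 7 days. SAP 7.1 makes that last date equal to the last dose date at final lock.

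The four exposure-adjusted AE tables in 6.4.1.4 carry no star, so they are overall only. SAP 6.2.6.1 adds that "eDiary zavegepant and LTT exposure is also tabulated by subgroup level and overall", and this includes patient-years.

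**The concern.** At final lock the time-on-zavegepant group is the observation window less 7 days. A subject followed for longer has more opportunity to record an AE, whatever the drug does. Protocol 6.6 also allows an AE or laboratory abnormality to end dosing, so the outcome helps decide the group. Subjects who stopped for an AE before Week 48 cannot be in the top group, so its discontinuation row is close to empty by construction.

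This is a long-term safety study, and readers will look to the longest-exposed group for reassurance. A rising any-AE row could be taken for cumulative toxicity. A vanishing discontinuation row could be taken for good long-term tolerability. Neither inference would be sound. Under SAP 8 these tables also go into the interim report supporting the new drug application, except those for the treated-migraine-day subgroup, which SAP 8 leaves out of that report.

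**Working it through.** **The plan's own figure.** SAP 5 gives an upper bound of 0.005 for zero events in 600. The exact value is 1 − 0.05^(1/600) = 0.00498, so it is reproduced. It is not affected by this point.

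**Inputs.** The group limits come from SAP 4.3, the 7-day tail from SAP 7.2, and the cap of 8 doses per 28 days from Protocol 7.2.2. The documents give no AE rate, dropout or stopping share for this study, so those are assumptions. No run gives the drug any exposure effect.

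**1. Observation length alone.** With a constant rate r per year and T weeks on drug, the percentage with any AE is 1 − exp(−r × (7T + 7)/365.25). For r = 0.5 and T = 6: 1 − exp(−0.5 × 49/365.25) = 6.5%. In the second row r is 2.0 for the first 12 weeks and 0.25 afterwards, an 8-fold fall.

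| T (group midpoint, weeks) | 6 | 18 | 30 | 42 | 50 |
|---|---|---|---|---|---|
| Constant 0.5 per year | 6.5% | 16.6% | 25.7% | 33.8% | 38.7% |
| 2.0, then 0.25 after Week 12 | 23.5% | 39.0% | 42.4% | 45.6% | 47.6% |

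The first row is a gradient with no exposure effect. The second still rises although the true rate has collapsed.

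**2. Adding AE-driven stopping (simulation).** Base case: 0.5 AE per patient-year, 35% dropout, 5% of AEs stop drug, about 4 sprays per 28 days, infrequent-use rule not enforced.

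| Final time on drug (weeks) | < 12 | 12-24 | 24-36 | 36-48 | ≥ 48 |
|---|---|---|---|---|---|
| Any AE | 8.9% | 18.8% | 27.2% | 35.0% | 37.6% |
| Discontinuation AE | 3.5% | 3.7% | 3.5% | 1.6% | 0.1% |

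Depending on how dosing and dropout are simulated, the first any-AE cell is about 8-11% and the last 37-38%. For discontinuation AEs the ends are about 3-6% and 0.1-0.2%. In a trial of 600 the discontinuation cells hold roughly 2.2, 1.9, 1.5, 1.5 and 0.4 subjects.

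The shape depends on the stopping share. At 1.0 AE per patient-year and 20% dropout, any AE is 11.4, 30.6, 44.0, 58.5 and 62.8% if no AE stops drug. It is 42.1, 51.8, 60.0, 57.9 and 54.4% if 20% do.

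**3. Cumulative sprays.** At even use, 80 sprays take 80/8 = 10 periods of 28 days, or 40 weeks, so this grouping is tied to time. In the base case any AE is 18.0, 32.8, 36.2, 37.4 and 36.8% from < 20 to ≥ 80 sprays. With the Protocol 6.6 infrequent-use rule always enforced it is 10.4, 27.1, 35.4, 37.3 and 38.0%. The distortion lies mainly in the lowest groups.

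**4. Does dividing by patient-years within the groups help?** Take a true rate of 1.0, 20% dropout and 10% of AEs stopping drug:
- events per patient-year within final-time groups: 2.68, 1.54, 1.29, 1.03, 0.89;
- events per patient-year by interval of onset, all subjects still at risk: 0.97, 0.95, 0.97, 0.96, 0.99.

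Only the second is close to the truth. With a true rate of 0.5 and 20% of AEs stopping drug, onset-interval rates are 0.45-0.47: a little low, but flat.

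**5. Average sprays and treated migraine days.** In the base case, any AE for < 6 versus ≥ 6 average sprays is 31.5 versus 31.6%; with the infrequent-use rule it is 24.3 versus 31.6%. For < 2 versus ≥ 2 treated migraine days it is 27.4 versus 32.4%, and 7.7 versus 29.7% with the rule, where median observation is 8.6 versus 48.4 weeks.

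**6. Laboratory tests.** SAP 6.4.2 schedules LFTs at "Screening; Pre-Baseline; all visits during the treatment period; early termination; and Follow-up Week 2". At an illustrative 0.5% per draw, 1 − 0.995^k gives 2.0% for 4 draws (Weeks 2, 4 and 8 plus early termination) and 6.8% for 14 (all treatment visits to Week 52). Hematology and general chemistry are drawn far less often: 2 versus 3 draws give 1.0 versus 1.5%.

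**The case against.** The strongest reply is that these are descriptive tables with no exposure-response test, and that patient-years by subgroup are shown elsewhere. It adds that any reader knows a subject dosing past Week 48 did not stop early. Disposition reasons, the overall discontinuation-AE table and the listings with treatment day also show AE-driven stopping. All of this is true and limits the severity. It does not repair the tables: patient-years expose unequal follow-up but, as step 4 shows, dividing by them leaves the stopping effect in place. The exposure-adjusted AE tables have no split by time.

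A reader might infer that LFT elevations are reported by these subgroups. The documents do not support that. The fold-ULN, exposure-adjusted and time-to-elevation tables in 6.4.2.2 carry no subgroup instruction. LFTs enter only through the worst-grade table of 6.4.2.1, and only if the Core SAP, which was not available, lists them as graded tests. The 0.5% per draw is also not anchored in the documents: Protocol 1.2.4.1 reports no subject with AST or ALT above 3x ULN in BHV3500-201.

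It is also tempting to delete every usage-defined table. That goes too far. The treated-migraine-day split can be as distorted as the spray split, and both can be handled with patient-years and a caution. Such a caution may already exist in the Core SAP or mock outputs, which could not be checked.

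**Conclusion.** The concern holds for the AE tables by final time on zavegepant, and to a lesser degree by cumulative sprays. The overlap between group and observation window follows from the SAP's own definitions. The direction and size of the artefact rest on assumed AE rates, dropout and stopping shares. Any-AE percentages can differ about 3.5- to 5-fold across time groups (38/11 to 37/8 in the base case) with no exposure effect. The discontinuation pattern is just as artificial but involves only a few subjects per group.

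The same reasoning applies to the worst-grade laboratory table, and to LFTs within it only on the condition above. A reader might also infer that the primary results are biased. They are not: the primary percentages are overall figures for the safety analysis set and do not use these subgroups. The change should be made, but the trial's main conclusion does not hang on it.

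**What to change.** 1. In SAP 6.4.1.2 and 6.4.1.4, replace the AE tables by final time on zavegepant with AEs, including those leading to discontinuation, by interval of onset from first dose: 0 to < 12, 12 to < 24, 24 to < 36, 36 to < 48 and ≥ 48 weeks. Give events per patient-year at risk and the number of subjects entering each interval. Run at-risk time to the study drug last date plus 7 days (to the data cut for ongoing subjects at the interim). Count repeat events as in the planned exposure-adjusted AE tables. Do not divide by patient-years within the final-time groups.
2. Keep the AE tables by cumulative sprays, average sprays and treated migraine days, and the laboratory tables by time and sprays, with patient-years beside the percentages. Footnote that the groups are defined after baseline; that they reflect length of observation, AE-driven stopping and the infrequent-use rule; and that they are not evidence of exposure-response.
3. Optionally, add to the time-to-LFT-elevation table in 6.4.2.2 the number of subjects tested in each interval as the denominator.

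The cost is SAP wording and some reprogramming of tables and mock outputs from data already collected. Crude AE percentages by final time on zavegepant would no longer be shown.

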#### 6.4.1.3 *Pre-treatment AEs*

Pre-treatment AEs are tabulated by SOC and PT for the enrolled analysis set for the following endpoints:

- AEs by intensity (total, mild, moderate, severe, moderate or severe, not reported)
- SAEs.

Pre-treatment AEs are tabulated by SOC and PT for the safety analysis set for the following endpoints:

- AEs by intensity
- SAEs.

#### 6.4.1.4 *On-treatment AEs*

On-treatment AEs are tabulated for the safety analysis set by SOC and PT for the following endpoints:

- AEs by intensity \*
- AEs occurring with  $\geq 5\%$  frequency by intensity (primary safety endpoint). The 5% cut applies only to total intensity.
- AEs occurring with  $\geq 10\%$  frequency
- TEAEs by intensity

- TEAEs occurring with  $\geq 2\%$  frequency after rounding. Percentages are displayed rounded to integers, and AEs are displayed in alphabetical order by SOC and PT.
- AEs related to study drug by intensity \*
- AEs by relationship to study drug (related, possibly related, unlikely related, not related, not reported)
- SAEs (primary safety endpoint)
- AEs leading to study drug discontinuation (primary safety endpoint)
- AEs of special interest
  - Potential drug abuse AEs, displayed in alphabetical order by intensity and PT without SOC (exploratory safety endpoint)
  - Medication-overuse headache AEs (exploratory safety endpoint)
  - Hepatic-related AEs by intensity (exploratory safety endpoint)
  - Local irritation AEs by intensity (exploratory safety endpoint)
  - Cardiovascular AEs
  - Suicidality AEs
- Exposure-adjusted multiple occurrences of unique AEs
- Exposure-adjusted multiple occurrences of unique SAEs
- Exposure-adjusted multiple occurrences of unique SAEs related to study drug
- Exposure-adjusted multiple occurrences of unique non-SAEs occurring with  $\geq 5\%$  frequency.

Endpoints marked with “\*” are also tabulated by subgroup level and overall for all subgroups of interest specified in Section 4.3.

Calculations for on-treatment exposure-adjusted multiple occurrences of unique AEs set the reference start date to the study drug start date, reference end date to the study drug end date, and reference last date to the study drug last date + 7 days.

#### 6.4.1.5 *Follow-up AEs*

Follow-up AEs are tabulated by SOC and PT for the follow-up analysis set for the following endpoints:

- AEs by intensity
- SAEs.

#### 6.4.1.6 AEs in All Safety Analysis Periods Combined

AEs in all safety analysis periods combined (i.e., pre-treatment, on-treatment, and follow-up) are tabulated by SOC and PT for the safety analysis set for the following endpoints:

- AEs leading to study drug discontinuation
- Hepatic-related AEs leading to study drug discontinuation
- Local irritation AEs leading to study drug discontinuation.

